5. SCHEDULE OF ACTIVITIES

The schedule of study activities is presented in [Table 1](#), [Table 2](#), [Table 3](#), and [Table 4](#).

CONFIDENTIAL

The information contained herein may not be used, disclosed, or published without the written consent of
Biogen MA Inc.

Table 1: Schedule of Activities During the Placebo-Controlled Period and the LTE Screening Period

Study Week	Baseline Screening Period ^{1, 2} within 65 days ³ of Day 1			Placebo-Controlled Period ⁴																				UV for Change in AD Medication ⁵	FUV ⁶
	S1	S2	S3 ⁸	1	4	8	12	16	20	24	28	32	36	40	44	48	52	56	60	64	68	72	76 EOT	78/EOS or ET ⁷	90
Study Day	S1	S2	S3 ⁸	1	29 ±7	57 ±7	85 ±7	113 ±7	141 ±7	169 ±7	197 ±7	225 ±7	253 ±7	281 ±7	309 ±7	337 ±7	365 ±7	393 ±7	421 ±7	449 ±7	477 ±7	505 ±7	533 ±7	547 ±7	631 ±7
Study day infusion ^{4, 9}				X	X	X	X	X	X	X	X	X	X	X	X	X	X	X	X	X	X	X	X		
Initial screening consent (optional) ¹⁰	X																								
Full informed consent ¹¹	X																						X ¹²	X ¹²	
Randomization				X																					
Eligibility criteria	X	X	X	X																			X ¹³	X ¹³	
NIA-AA criteria review	X																								
Medical history	X	X	X	X																					
Body weight	X			X	X	X	X			X				X			X			X			X	X	X
Height	X																								
Pregnancy test ¹⁴	X			X	X	X	X	X	X	X	X	X	X	X	X	X	X	X	X	X	X	X	X	X	X
Follicle-stimulating hormone ¹⁵	X																								
Alcohol/drug screen	X																								
HbA1c	X																								

CONFIDENTIAL

The information contained herein may not be used, disclosed, or published without the written consent of Biogen MA Inc.

Study Week	Baseline Screening Period ^{1, 2} within 65 days ³ of Day 1			Placebo-Controlled Period ⁴																				UV for Change in AD Medication ⁵	FUV ⁶	
	S1	S2	S3 ⁸	1	4	8	12	16	20	24	28	32	36	40	44	48	52	56	60	64	68	72	76 EOT			78/ EOS or ET ⁷
Study Day	S1	S2	S3 ⁸	1	29 ±7	57 ±7	85 ±7	113 ±7	141 ±7	169 ±7	197 ±7	225 ±7	253 ±7	281 ±7	309 ±7	337 ±7	365 ±7	393 ±7	421 ±7	449 ±7	477 ±7	505 ±7	533 ±7	547 ±7	631 ±7	
HIV ¹⁶ /hepatitis tests	X																									
Physical examination	X			X			X			X					X							X		X		X
Neurological examination	X			X			X			X					X							X		X		X
12-lead paper ECG ¹⁸	X			X			X			X					X							X		X		X
Vital signs ¹⁹	X			X	X	X	X	X	X	X	X	X	X	X	X	X	X	X	X	X	X	X	X	X	X	X
Hematology/ clinical chemistry/ urinalysis	X			X			X			X					X							X		X		X
Blood sample for anti-BIIB092 Ab ⁴				X	X					X					X								X			X

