6. STUDY OBJECTIVES AND ENDPOINTS

Placebo-Controlled Period Objectives and Endpoints	
Primary Objective	Primary Endpoint
To evaluate the safety and tolerability of BIIB092 in participants with MCI due to AD or with mild AD	Incidence of AEs and SAEs during the placebo-controlled period
Secondary Objectives	Secondary Endpoints
To evaluate the efficacy of multiple doses of BIIB092 in slowing cognitive and functional impairment in participants with MCI due to AD or with mild AD. This is the primary efficacy objective	Change from Baseline over time at Week 78 on the CDR-SB. This is the primary efficacy endpoint
To evaluate the immunogenicity of BIIB092 after multiple doses in participants with MCI due to AD or with mild AD	Incidence of anti-BIIB092 antibodies in serum over time up to Week 90
Exploratory Objectives	Exploratory Endpoints
To assess the effect of BIIB092 on the clinical progression of AD	Changes from Baseline over time up to Week 78 on the Mini-Mental State Examination (MMSE), International Shopping List Test Immediate Recall (ISLT), Category Fluency and Letter Fluency tests from the Delis-Kaplan Executive Function System (DKEFS), Digit Symbol Substitution Test (DSST), Trail Making Test, Part A (Trails A), Everyday Cognition (eCog), Alzheimer's Disease Cooperative Study-Activities of Daily Living (ADCS-ADL), Functional Activities Questionnaire (FAQ), Alzheimer's Disease Assessment Scale-Cognitive (ADAS-Cog 13 [13 item]), and Neuropsychiatric Inventory-10 (NPI-10)
To assess the effect of BIIB092 on changes in caregiver burden and participant quality of life	Changes from Baseline over time up to Week 68 on the Zarit Burden Interview (ZBI) and Quality of Life for Alzheimer's Disease (QoL-AD)

CONFIDENTIAL

The information contained herein may not be used, disclosed, or published without the written consent of Biogen MA Inc.

To assess the effect of BIIB092 on resource utilization
	
Resource Utilization in Dementia-Lite Version (RUD-Lite) results over time up to Week 68

To assess BIIB092 PK in serum in participants with MCI due to AD or with mild AD
	
Trough serum BIIB092 concentrations and end-of-infusion serum BIIB092 concentrations from the samples collected at the visits indicated in the Schedule of Activities

[REDACTED]
	
[REDACTED]

[REDACTED]
	
[REDACTED]

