5.8 Additional Exploratory Endpoints

5.8.1 Health Outcomes

The FAS will be used for the analysis of health outcomes data for LTE period. The result will be listed by LTE treatment group for placebo-controlled and LTE period.

CONFIDENTIAL

The information contained herein may not be used, disclosed, or published without the written consent of Biogen MA Inc.

6 Appendix I: Visit Window Mapping

For data that are summarized by visit and longitudinal analysis, assessment from all scheduled visits including EOT visit and EOS visit, and all unscheduled visits will be mapped to an appropriate analysis visit using a windowing scheme. Analysis visit windows are defined in [Table 1 - Table 12] for different endpoints.

If there are 2 or more assessments from visits other than EOT or EOS visits mapped to the same analysis visit for a subject, the assessment that is closest to the target visit day will be used for analysis. If there are 2 or more assessments from visits other than EOT or EOS visits mapped to the same analysis visit with the same distance from the target visit day, then select the later one(s) for the analysis. If there are 2 or more assessments from visits other than EOT or EOS visits mapped to the same analysis visit and on the same day, use the average value for quantitative parameters and the worst value for qualitative parameters for analysis.

Table 1. Visit Windows for Efficacy Endpoints

Efficacy Endpoint	Analysis visit	Target visit day	Analysis visit window
CDR, NPI-10, ADAS-Cog13, FAQ, and ADCS-ADL	Baseline	1	Most recent non-missing pre-dose value
	Week 24	169	[2, 267]
	Week 52	365	[268, 456]
	Week 78	547	[457, the end day of the placebo-controlled period ¹]
	Week 104	729	[one day after the start day of the LTE period ² , 813]
	Week 128	897	[814, 981]
	Week 152	1065	[982, 1149]
	Week 176	1233	[1150, 1317]
	Week 200	1401	[1318, 1492]
	Week 226	1582	≥1493
ISLT, DKEFS, DSST, Trails A,	Baseline800-	1	Most recent non-missing pre-dose value
	Week 12	85	[2, 141]
	Week 28	197	[142, 239]
	Week 40	281	[240, 337]
	Week 56	393	[338, 435]
	Week 68	477	[436, 512]
	Week 78	547	[513, the end day of the placebo-controlled period ¹]
	Week 108	757	[one day after the start day of the LTE period ² , 841]

CONFIDENTIAL

The information contained herein may not be used, disclosed, or published without the written consent of Biogen MA Inc.

Efficacy Endpoint	Analysis visit	Target visit day	Analysis visit window
	Week 132	925	[842, 1009]

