	Week 156	1093	[1010, 1261]
	Week 204	1429	[1262, 1506]
	Week 226	1582	≥1507
eCog	Baseline	1	Most recent non-missing pre-dose value
	Week 28	197	[2, 295]
	Week 56	393	[296, 470]
	Week 78	547	[471, the end day of the placebo-controlled period ¹]
	Week 108	757	[one day after the start day of the LTE period ² , 841]
	Week 132	925	[842, 1009]
	Week 156	1093	[1010, 1261]
	Week 204	1429	[1262, 1506]
	Week 226	1582	≥1507
MMSE	Baseline	1	Most recent non-missing pre-dose value
	Week 12	85	[2, 127]
	Week 24	169	[128, 225]
	Week 40	281	[226, 323]
	Week 52	365	[324, 421]
	Week 68	477	[422, 512]
	Week 78	547	[513, the end day of the placebo-controlled period ¹]
	Week 104	729	[one day after the start day of the LTE period ² , 813]
	Week 128	897	[814, 981]
	Week 152	1065	[982, 1149]
	Week 176	1233	[1150, 1317]
	Week 200	1401	[1318, 1492]
	Week 226	1582	≥1493

1 The end day of the placebo-controlled period is the last day on or before the first infusion in LTE for subjects who enter LTE and is the last day in study for subjects who do not enter LTE. 2 The start day of the LTE period is the day of the first infusion in the LTE period.
			

CONFIDENTIAL

The information contained herein may not be used, disclosed, or published without the written consent of Biogen MA Inc.

Table 2. Visit Windows for Laboratory by Visit Summaries using Placebo-Controlled Baseline

Analysis visit	Target visit day	Analysis visit window
Baseline	1	Most recent non-missing pre-dose value
Week 12	85	[2, 127]
Week 24	169	[128, 253]
Week 48	337	[254, 421]
Week 72	505	[422, 526]
Week 78	547	[527, 630* or the end day of the placebo-controlled period ¹]
Week 90*	631	[631, the last day in the study]
Week 100	701	[the start day of the LTE period ² , 785]
Week 124	869	[786, 953]
Week 148	1037	[954, 1121]
Week 172	1205	[1122, 1289]
Week 196	1373	[1290, 1457]
Week 220	1541	[1458, 1562]
Week 226	1582	[1563, 1625]
Week 238	1667	≥1626

* Applicable only for the subjects who do not go to LTE. They are expected to have week 90 follow-up assessment.
 1 The end day of the placebo-controlled period is the last day before the first infusion in LTE for subjects who enter LTE and is the last day in study for subjects who do not enter LTE.
 2 The start day of the LTE period is the day of the first infusion in the LTE period.

Table 3. Visit Windows for Laboratory by Visit Summaries using LTE Baseline

Analysis visit	Target visit day	Analysis visit window	Protocol visit

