1 The end day of the placebo-controlled period is the last day before the first infusion in LTE for subjects who enter LTE and is the last day in study for subjects who do not enter LTE.
2 The start day of the LTE period is the day of the first infusion in the LTE period.

Table 7. Visit Windows for ECG by Visit Summaries using LTE Baseline

Analysis visit	Target visit day	Analysis visit window	Protocol visit
Baseline	Most recent non-missing value prior to the first infusion in LTE	Most recent non-missing value prior to the first infusion in LTE	Week 78

CONFIDENTIAL

The information contained herein may not be used, disclosed, or published without the written consent of Biogen MA Inc.

Analysis visit	Target visit	visit	Analysis visit window	Protocol visit
Week 24	169		[the start day of the LTE period, 253]	Week 104
Week 48	337		[254, 421]	Week 128
Week 72	505		[422, 589]	Week 152
Week 104	673		[590, 757]	Week 176
Week 128	841		[758, 932]	Week 200
Week 152	1023		[933, 1065]	Week 226
Week 176	1107		>1065	Week 238

Day 1 is the first infusion day in LTE period

Table 8. Visit Windows for Vital Sign by Visit Summaries using Placebo-Controlled Baseline

Analysis visit	Target visit day	Analysis visit window
Baseline	1	Most recent non-missing pre-dose value
D1 Post dose	1	Day 1 post dose infusion (if more than one Day 1 post dose results available, the average of the available results will be used)
Week 4– Pre dose	29	[2, 43] (Pre-dose assessment)
Week 4- Post dose	29	[2, 43] (Post dose assessment)
Week 8– Pre dose	57	[44, 71] (Pre-dose assessment)
Week 8- Post dose	57	[44, 71] (Post dose assessment)
Week 12– Pre dose	85	[72, 99] (Pre-dose assessment)
Week 12- Post dose	85	[72, 99] (Post dose assessment)
Week 16	113	[100, 127]
Week 20	141	[128, 155]
Week 24	169	[156, 183]
Week 28	197	[184, 211]
Week 32	225	[212, 239]
Week 36	253	[240, 267]
Week 40	281	[268, 295]
Week 44	309	[296, 323]
Week 48	337	[324, 351]
Week 52	365	[352, 379]
Week 56	393	[380, 407]
Week 60	421	[408, 435]
Week 64	449	[436, 463]
Week 68	477	[464, 491]
Week 72	505	[492, 519]
Week 76	533	[520, 540]
Week 78	547	[541, 589* or the end day of the placebo-controlled period ¹]
Week 90*	631	[590, the last day in the study]
Week 80	561	[the start day of the LTE period ² , 575]
Week 84	589	[576, 603]
Week 88	617	[604, 631]
Week 92	645	[632, 659]
Week 96	673	[660, 687]

CONFIDENTIAL

The information contained herein may not be used, disclosed, or published without the written consent of Biogen MA Inc.

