Week 20	141	[128, 155]	Week 100
Week 24	169	[156, 183]	Week 104
Week 28	197	[184, 211]	Week 108
Week 32	225	[212, 239]	Week 112
Week 36	253	[240, 267]	Week 116
Week 40	281	[268, 295]	Week 120
Week 44	309	[296, 323]	Week 124
Week 48	337	[324, 351]	Week 128
Week 52	365	[352, 379]	Week 132
Week 56	393	[380, 407]	Week 136
Week 60	421	[408, 435]	Week 140
Week 64	449	[436, 463]	Week 144
Week 68	477	[464, 491]	Week 148
Week 72	505	[492, 519]	Week 152
Week 76	533	[520, 547]	Week 156
Week 80	561	[548, 575]	Week 160
Week 84	589	[576, 603]	Week 164
Week 88	617	[604, 631]	Week 168
Week 92	645	[632, 659]	Week 172
Week 96	673	[660, 687]	Week 176
Week 100	701	[688, 715]	Week 180
Week 104	729	[716, 743]	Week 184
Week 108	757	[744, 771]	Week 188
Week 112	785	[772, 799]	Week 192
Week 116	813	[800, 827]	Week 196
Week 120	841	[828, 855]	Week 200
Week 124	869	[856, 883]	Week 204
Week 128	897	[884, 911]	Week 208
Week 132	925	[912, 939]	Week 212
Week 136	953	[940, 967]	Week 216
Week 140	981	[968, 995]	Week 220
Week 144	1009	[996, 1023]	Week 224
Week 148	1037	[1024, 1051]	Week 226
Week 152	1065	[1052, the end day of the LTE period]	Week 238

CONFIDENTIAL

The information contained herein may not be used, disclosed, or published without the written consent of Biogen MA Inc.

Table 10. Visit Windows for ADA data using Placebo controlled baseline

Analysis visit	Target visit day	Analysis visit window
Baseline	1	See baseline definition in Section 3.7.1
Week 4	29	[2, 99]
Week 24	169	[100, 253]
Week 48	337	[254, 435]
Week 76	533	[436, the end day of the placebo-controlled period ¹]
Week 80	561	[the start day of the LTE period ² , 645]
Week 104	729	[646, 771]
Week 116	813	[772, 953]
Week 156	1093	[954, 1163]
Week 176	1233	[1164, 1303]
Week 196	1373	[1304, 1471]
Week 224	1569	[1472, 1618]
Week 238	1667	≥1619

1 The end day of the placebo-controlled period is the last day before the first infusion in LTE for subjects who enter LTE, and is the last day in study for subjects who do not enter LTE.
 2 The start day of the LTE period is the day of the first infusion in the LTE period.

Table 11. Visit Windows for ADA data using LTE Baseline

Analysis visit	Target visit day	Analysis visit window	Protocol visit
Baseline	Most recent non-missing value prior to the first infusion in LTE	Most recent non-missing value prior to the first infusion in LTE	Week 80
Week 24	169	[2, 253]	Week 104
Week 48	337	[254, 435]	Week 116
Week 76	533	[436, 631]	Week 156
Week 104	729	[632, 771]	Week 176

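### SAP visit windows put early Week 90 laboratory and ECG visits in Week 78, all Week 90 ADA samples in Week 76 and, if Table 11 is used, on-time Week 116 ADA samples in Week 104

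*SAP*

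**What the plan says.** **Week 90 visit.** Protocol Table 1 places the follow-up visit for treatment completers who do not enter the LTE at Day 631 ±7. Its row "Blood sample for anti-BIIB092 Ab" includes a sample at that visit. Protocol Section 13.6, which lists the ADA sampling times, does not name Week 90.

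**Laboratory and ECG (SAP Appendix I, Tables 2 and 6).** Week 78 (target 547) is "527, 630* or the end day of the placebo-controlled period" and Week 90 (target 631) is "631, the last day in the study". The asterisk marks subjects who do not go on to the LTE.

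**Vital signs (Table 8).** With the same targets, Week 78 ends at 589 and Week 90 is "590, the last day in the study".

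**ADA, placebo-controlled baseline (Table 10).** Week 76 is "436, the end day of the placebo-controlled period". The footnote says this end day "is the last day in study for subjects who do not enter LTE". No Week 90 row follows.

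**Choice of record.** The closest-to-target rule begins "If there are 2 or more assessments from visits other than EOT or EOS visits mapped to the same analysis visit for a subject".

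**ADA, LTE baseline (Table 11).** Day 1 is the first LTE infusion. The protocol Week 104 row is [2, 253]. The protocol Week 116 row has target 337 and window [254, 435]. Table 9 (vital signs, LTE baseline) gives protocol Week 116 target 253 and window [240, 267].

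**The concern.** A visit window should hold the days the protocol allows for that visit. These windows do not, and the SAP's own neighbouring tables show a different treatment of the same target days. Week 90 is 14 weeks after the last dose, whereas Week 76 is a dosing visit and Week 78 follows it by two weeks. Under the present windows the Week 90 laboratory and ECG rows lose visits made 1 to 7 days early, and the by-visit ADA table cannot show Week 90 at all. If Table 11 is used, on-schedule Week 116 ADA samples drop out of the by-visit table, because the Week 104 sample in the same window lies closer to the target.

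**Working it through.** **Inputs.** Target study day = 7 × week + 1, which gives Week 76 = 533, Week 78 = 547, Week 80 = 561, Week 90 = 631, Week 104 = 729 and Week 116 = 813. Each visit has ±7 days (Protocol Tables 1 and 2). LTE day = study day − (study day of first LTE dose) + 1.

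**1. The SAP's boundary rule.** The fixed boundaries between adjacent visits are midpoints of target days. In Table 2: (85+169)/2 = 127, (169+337)/2 = 253, (337+505)/2 = 421, (505+547)/2 = 526, all as printed. For Weeks 78 and 90 the rule gives (547+631)/2 = 589. Table 8 prints 589; Tables 2 and 6 print 630, which is the Week 90 target minus one.

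**2. Laboratory and ECG.** The allowed Week 90 days are 624-638, which is 15 days. Days 624-630 (7 of 15) fall in Week 78 and days 631-638 (8 of 15) in Week 90. The misplaced days lie 624−547 = 77 to 630−547 = 83 days from the Week 78 target, but only 1 to 7 days from the Week 90 target.

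**3. ADA, Table 10.** For a subject not entering the LTE, Week 76 runs from Day 436 to the last day in study. All 15 allowed days (624-638) fall in it. The midpoint rule would end Week 76 at (533+631)/2 = 582.

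**4. Which record is kept.** In these windows the other record is the Week 78/EOS visit (laboratory, ECG) or the Week 76/EOT visit (ADA). The closest-to-target rule is written for visits other than EOT or EOS, so the choice is undefined. If the rule were applied anyway, the Week 90 record would normally lose and would stand under the earlier label only when the EOS or EOT record is missing.

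**5. ADA, Table 11.** With LTE Day 1 on study day 561, Week 116 is 813−561+1 = LTE Day 253, the last day of the Week 104 row. The allowed days are 246-260:

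| LTE days | Row assigned | Count |
|---|---|---|
| 246-253 | Week 104 | 8 of 15 |
| 254-260 | Week 116 | 7 of 15 |

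The printed target is 337−253 = 84 days too late. A sample on Days 246-253 is 77-84 days from target 169, while a Week 104 sample within ±7 is at most 7 days away, so the Week 104 sample is kept whenever it exists. The result depends on the date of the first LTE dose: on study day 554 the Week 116 days are 253-267 (1 of 15 misplaced), and on study day 568 they are 239-253 (15 of 15).

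**6. Corrected Table 11.** The true LTE days for protocol Weeks 104, 116, 156, 176, 196, 224 and 238 are 169, 253, 533, 673, 813, 1009 and 1107. Midpoints are 211, 393, 603, 743, 911 and 1058, which equal the Table 10 bounds 771, 953, 1163, 1303, 1471 and 1618 minus 560. These windows hold 15 of 15 allowed days in every row for first LTE doses on study days 554, 561 and 568.

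**The case against.** **Impact of the Week 90 error.** It needs a BIIB092-treated completer who declines the LTE and, for laboratory and ECG, a visit 1-7 days early. A reader might infer that off-drug values are being reported as Week 78 or Week 76. That happens only if the EOS or EOT record is missing or not selected; otherwise the Week 90 row is simply thinner. This limits the consequence but does not make the windows right.

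**Who is affected.** A reader might extend the point to everyone who does not enter the LTE. Day 631 ±7 applies to treatment completers. Early discontinuers have their follow-up visit 14 weeks after their last dose, on other days, and moving these cuts would not place those visits.

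**ADA at Week 90.** Table 10 matches the sampling list in Protocol Section 13.6, which omits Week 90. The protocol therefore disagrees with itself, and its two schedules have to be reconciled first. The protocol endpoint "Incidence of anti-BIIB092 antibodies in serum over time up to Week 90" belongs to the placebo-controlled period, which has a separate SAP that was not supplied and may report Week 90. The documents do not support a claim that this endpoint goes unreported.

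**Table 11.** SAP Section 5.7.1 uses the placebo-controlled baseline for ADA and does not name Table 11; Table 10 places Week 116 correctly. This objection stands, so the point is conditional. Use of Table 11 remains plausible because the by-visit ADA table covers the active treatment period, whose Day 1 for late-start subjects is the first LTE dose (SAP Section 3.4).

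**The Week 104 interim cut.** Since eCog and the EMACC components are first scheduled in the LTE at Week 108, a reader might infer a further window error. The cut is a stated data limit, and unscheduled or early-termination visits can supply some of these records, so it is not part of this point.

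**Conclusion.** The windows are wrong as written, with limited consequence. For treatment completers not entering the LTE, 7 of 15 allowed Week 90 days are labelled Week 78 in Tables 2 and 6, and 15 of 15 are labelled Week 76 in Table 10. If Table 11 is used, 8 of 15 allowed Week 116 days fall in the Week 104 row when the first LTE dose is on study day 561 (range 1 to 15 over the allowed Week 80 window).

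These are counts of allowed days, not shares of samples. The documents give neither the distribution of visit dates nor the number of completers who do not enter the LTE. If Table 11 serves late-start subjects, they come from the placebo arm (176 of 528 planned; 654 subjects were randomized in all, and the number entering the LTE is not given).

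Only by-visit summaries are affected. AE incidence, CDR-SB, the laboratory shift and potentially-clinically-significant analyses (which use all values), the per-patient ADA response table and the listings are not. Table 11 also places Week 238 (LTE Day 1107) in its Week 224 row, but SAP Section 5.6.2 says no subject reached Week 226, so that has no practical effect.

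**What to change.** 1. **Tables 2 and 6**, subjects not entering the LTE: end Week 78 at Day 589 and start Week 90 at Day 590, as in Table 8.
2. **ADA at Week 90:** reconcile Protocol Section 13.6 with Protocol Table 1. If the Week 90 sample stands, end Week 76 in SAP Table 10 at Day 582 for these subjects and add a Week 90 row from Day 583 to the last day in study.
3. **Selection rule:** state which record is used when an EOT or EOS record shares a window with another record.
4. **Table 11:** state whether it is used, and for whom, given the baseline in Section 5.7.1. If it is kept, use targets 169, 253, 533, 673, 813, 1009 and 1107 with windows [2, 211], [212, 393], [394, 603], [604, 743], [744, 911], [912, 1058] and ≥1059. Relabel the analysis visits as LTE Weeks 24, 36, 76, 96, 116, 144 and 158.

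The cost is two rows in each of Tables 2, 6 and 10, one selection rule, one sentence on Table 11 (or one rebuilt table), the protocol reconciliation, and a rerun of any by-visit output already programmed on the present windows.
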